8.2.2 Immune Mediated Adverse Events (IMAEs) *(to Support US BLA)*

Immune-mediated AEs (IMAE) are AEs consistent with an immune-mediated mechanism or immune-mediated component for which non-inflammatory etiologies (eg, infection or tumor progression) have been ruled out. IMAEs can include events with an alternate etiology which were exacerbated by the induction of autoimmunity. To be specific, IMAEs are events (or groups of PTs describing specific events) that include pneumonitis, diarrhea/colitis, hepatitis, nephritis/renal dysfunction, rash, endocrine (adrenal insufficiency, hypothyroidism/thyroiditis, hypothyroidism, thyroiditis, hyperthyroidism, diabetes mellitus and hypophysitis), and other specific events, considered as potential immune-mediated events by investigator that meet the definition summarized below:

- those occurring within extended treatment-emergent period,

- regardless of causality,
- treated with immune-modulating medication (of note, endocrine AEs such as adrenal insufficiency, hypothyroidism/thyroiditis, hypothyroidism, thyroiditis, hyperthyroidism, diabetes mellitus, and hypophysitis are considered IMAEs regardless of immune-modulating medication use, since endocrine drug reactions are often managed without immune-modulating medication),
- with no clear alternate etiology based on investigator assessment, or with an immune-mediated component

The list of MedDRA preferred terms used to identify IMAEs is revisited quarterly and updated accordingly. The preferred terms used for the selection at the time of the database lock by categories will be provided.

IMAEs will be summarized using the extended treatment-emergent period for each immune-mediated category for Arm A only:

- Overall summary of non-endocrine IMAEs by worst CTC grade (any grade, grade 3-4, grade 5) where immune-modulating medication was initiated presented by category / PT.
- Overall summary of endocrine IMAEs by worst CTC grade (any grade, grade 3-4, grade 5) presented by category / PT
- Overall summary of non-endocrine IMAEs leading to study drug discontinuation by worst CTC grade (any grade, grade 3-4, grade 5) where immune modulating medication was initiated presented by category / PT
- Overall summary of endocrine IMAEs leading to study drug discontinuation by worst CTC grade (any grade, grade 3-4, grade 5) presented by category / PT
- Overall summary of non-endocrine IMAEs leading to study drug dose delay or reduction by worst CTC grade (any grade, grade 3-4, grade 5) where immune modulating medication was initiated presented by category / PT
- Overall summary of non-endocrine IMAEs leading to study drug dose delay by worst CTC grade (any grade, grade 3-4, grade 5) where immune modulating medication was initiated presented by category / PT
- Overall summary of non-endocrine IMAEs leading to study drug dose reduction by worst CTC grade (any grade, grade 3-4, grade 5) where immune modulating medication was initiated presented by category / PT
- Overall summary of endocrine IMAEs leading to study drug dose delay or reduction by worst CTC grade (any grade, grade 3-4, grade 5) presented by category / PT
- Overall summary of endocrine IMAEs leading to study drug dose delay by worst CTC grade (any grade, grade 3-4, grade 5) presented by category / PT

- Overall summary of endocrine IMAEs leading to study drug dose reduction by worst CTC grade (any grade, grade 3-4, grade 5) presented by category / PT
- Summaries of time-to onset and time-to resolution of non-endocrine IMAEs where immune modulating medication was initiated presented by category
- Summaries of time-to onset and time-to resolution of endocrine IMAEs presented by category.

A by-patient listing of IMAEs will be provided. By-patient listings of time-to resolution for longest IMAEs cluster (any grade and grade 3-5 in separate summaries) will also be provided.

8.2.3 Other Events of Special Interest

Other events of special interest (OEOSI, also known as other immune-related adverse events of special interest) consist of a list of preferred terms grouped by specific category (e.g. Myositis Event, Myocarditis Event, Demyelination Event, Guillain-Barre Syndrome, Pancreatitis Event, Uveitis Event, Encephalitis Event, Myasthenic Syndrome, Rhabdomyolysis Event, Graft Versus Host Disease).

The list of MedDRA preferred terms used to identify OEOSI is revisited quarterly and updated accordingly. The preferred terms used for the selection at the time of the database lock by categories will be provided.

OEOSI will be summarized by treatment arm for each category.

The following analyses will be conducted using the extended treatment-emergent period:

- Overall summary of OEOSI by worst CTC grade (any grade, grade 3-4, grade 5) presented by category / PT
- Overall summary of drug-related OEOSI by worst CTC grade (any grade, grade 3-4, grade 5) presented by category / PT

A by-patient listing of OEOSI will be provided.

8.3 Adverse Events for NKTR-214

8.3.1 Adverse Event of Special Interest for NKTR-214

Adverse events of special interest for NKTR-214 consists of ischemic cerebrovascular events (ICE). All analyses will be conducted in the Safety I/P-risk population and the Safety all-risk population by treatment arm using the treatment-emergent period. Search list used to identify ICE will be provided.

The following analyses will be conducted for ICE:

- Overall summary of ICE by worst CTC grade (any grade, grade 3-4, grade 5) presented by PT
- Overall summary of any serious ICE by worst CTC grade (any grade, grade 3-4, grade 5) presented by PT
- Overall summary of any ICE leading to discontinuation of study therapy by worst CTC grade (any grade, grade 3-4, grade 5) presented by PT
- Overall summary of any ICE leading to discontinuation of NKTR-214 by worst CTC grade (any grade, grade 3-4, grade 5) presented by PT. This summary will be conducted for Arm A patients only.
- Time-to onset of ICE (any grade, grade 3-5)

Time-to onset analyses are restricted to treated patients who experienced at least one ICEs.

A by-patient listing of ICE will be provided.

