2.3.2.2 Updated Analysis of CVA Events Observed with NKTR-214

A cumulative search of the NKTR-214 global safety database was conducted on 28 October 2020, which included 1345 patients who received NKTR-214 in triplet combinations with nivolumab plus ipilimumab or with nivolumab plus NKTR-262 (a toll-like receptor agonist 7/8); in doublet combinations with checkpoint inhibitors; in a doublet combination (NKTR-214 with nivolumab) plus chemotherapy, and in combination with NKTR-262 from the following studies: 15-214-01, 16-214-02, 16-214-05, 17-214-09, 18-214-10, 20-214-29, CA045-001 (17-214-08), CA045-009 (18-214-03), CA043-010 (18-214-14), SP-IND, and 17-262-01.

Overall, 1.9% (26 of 1345) of patients exposed to NKTR-214 reported CVA events. Of the 26 patients, 13 patients experienced Grade 3 or 4 events and 4 patients had a fatal outcome. The mean time to first CVA event was 218.7 days (range 4 to 727 days; median 158 days). Twenty of the 26 patients with CVA events received a doublet combination with a checkpoint inhibitor, which included 1.7% (19 of 1116) of patients who received nivolumab, 1.3% (1 of 76) who received pembrolizumab, and 0% (0 of 23) who received atezolizumab.

Based on these events, CVA was escalated to an adverse event of special interest (AESI) in 2020 and mitigations were put in place to reduce the risk of CVA. These mitigations include implementation of a CVA adverse event management algorithm ([Appendix 6](#)) and updates to the exclusion criteria, renal function and hydration assessment, hydration guidelines, concomitant and prohibited medications, dose modification guidelines, and discontinuation criteria. Additional information on the clinical safety and risk of CVA is found in the NKTR-214 Investigator's Brochure.

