8.11 Adverse Events of Special Interest

The AEs listed below are considered AESIs. Regardless of the assessment of whether the AESI is serious or nonserious, all AESIs are required to follow the timeline for SAE reporting (within 24 hours as described in Section 8.7) from the sites to Nektar Drug Safety: [contact].

- CVA events (including TIA; any grade; CVA Management Guidelines are provided in [Appendix 6](#))

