For patients off treatment, the treatment-emergent period is defined as the period of time on or after the day (and time, if collected and not missing) of the first dose of study treatment, until: the date of (initiation of new anticancer therapy – 1 day) or (30 days after the date of the last dose of any study treatment), whichever is earlier.

The extended treatment-emergent period will be defined as the period of time on or after the day (and time, if collected and not missing) of the first dose of study treatment until earlier date of (initiation of new anticancer therapy – 1 day) and (100 days after the date of the last dose of any study treatment).

- **Treatment-Emergent Adverse Event (TEAE):**

TEAEs are AEs with an onset date (and time, if collected and not missing) within the treatment-emergent period, or extended treatment-emergent period depending on the analysis

Incomplete start and end dates for TEAEs will be imputed. Any AE will be considered as a TEAE if its status cannot be fully determined because of incomplete data.

- **Last Known Alive Date:** Last known alive date will be defined as the latest alive date on or before data cutoff date, captured from multiple sources. Note that if there is an event date (either an assessment or death) beyond the data cutoff date, the last known alive date will be the data cutoff date. If a patient died before or on the data cutoff date, the last known alive date will be set as the death date. The last known alive date will not be imputed, except in the case that the death date is partially missing (see details in Section 6.4)

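### SAP 8.3.1 tabulates the NKTR-214 AESI as ischemic events to 30 days after last dose, but the protocol's AESI is any CVA or TIA, with collection to 100 days

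*SAP*

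**What the plan says.** **Protocol.** Section 8.11 lists one AESI: "CVA events (including TIA; any grade"), whether serious or not. Section 8.2 collects adverse events to 100 days after the last dose of all study drugs. Section 8.7 collects serious events to the same day even if another anticancer therapy has started.

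**SAP.** Section 8.3.1 states: "Adverse events of special interest for NKTR-214 consists of ischemic cerebrovascular events (ICE"). The analyses are run "by treatment arm using the treatment-emergent period". Section 6.6 ends that period, for patients off treatment, at the earlier of the day before new anticancer therapy and "30 days after the date of the last dose of any study treatment". The extended period in the same section replaces 30 days by 100 but keeps the cut at new therapy. On scope, 8.3.1 says "Search list used to identify ICE will be provided"; the list is not in the SAP. The planned ICE outputs are counts by worst grade and preferred term, time to onset among patients who had an event, and a listing.

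**Other windows in the SAP.** For other events of special interest, 8.2.3 says: "The following analyses will be conducted using the extended treatment-emergent period". Immune-mediated events (8.2.2) and abnormal hepatic function tests (8.5.4) also use the extended period. Select adverse events (8.2.1.1) and the other NKTR-214 safety observations (8.3.2) use the shorter one.

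**The concern.** Protocol 2.3.2.2 explains that CVA was made an AESI because of events seen across the program: 26 patients, 4 with a fatal outcome. A reader will take the SAP's AESI table as the count for that signal. It is a subset in two respects. Its label covers only ischemic events, and its window stops up to 70 days before collection does. It can equal the protocol's AESI count but cannot exceed it.

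Two uses of the table are affected. One is the comparison between arms: Protocol 2.4.1 lists bleeding among common sunitinib reactions, so non-ischemic events matter there. The other is comparison with the program rates in Protocol 2.3.2, which are given for CVA without an ischemic restriction.

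**Working it through.** **1. The plan's own rates (Protocol 2.3.2.2).** 26/1345 = 1.93% (stated 1.9%). With nivolumab, 19/1116 = 1.70% (stated 1.7%). Both reproduce.

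**2. Expected events in Arm A (300 patients per arm, Protocol synopsis).** 0.017 × 300 = 5.1. At the overall rate, 26/1345 × 300 = 5.8.

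**3. Weight of one event.** 1/5.1 is about 20% of the estimate. With exact 95% intervals:

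| Events in 300 | Incidence | 95% CI |
|---|---|---|
| 5 | 1.7% | 0.5 to 3.8% |
| 4 | 1.3% | 0.4 to 3.4% |
| 3 | 1.0% | 0.2 to 2.9% |

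**4. How much at-risk time lies in days 31 to 100.** The documents give no distribution of CVA onset relative to last dose. They give only "The mean time to first CVA event was 218.7 days (range 4 to 727 days; median 158 days"). Assume a constant hazard and no new therapy. The share of time at risk (to last dose + 100 days) that falls in the last 70 days is 70/(exposure days + 100):

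| Assumed mean exposure | Share |
|---|---|
| 3 months | 70/191.3 = 37% |
| 6 months | 70/282.6 = 25% |
| 12 months | 70/465.3 = 15% |
| 24 months | 70/830.5 = 8% |

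**5. Range of the loss.** Assume a non-ischemic share of 0 to 30% and a late share of 0 to 25%. Events kept = 5.1 × (1 − non-ischemic share) × (1 − late share). This runs from 5.1 (no loss) to 5.1 × 0.70 × 0.75 = 2.7. Neither share is given in the documents.

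**6. Whether other outputs fill the gap.**

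| Output | What it lacks |
|---|---|
| All and serious TEAEs by SOC and PT (SAP 8.1) | CVA terms not grouped; 30-day window |
| 100-day repeats (SAP 8.1) | Drug-related and NKTR-214-related events only |
| Deaths in the extended period (SAP 8.4) | Non-fatal CVAs |
| Listings (SAP 8.0) | No incidence by arm |

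The restriction to related events matters. In Protocol 2.3.2.1, 9 doublet patients had a CVA, and in 4 of them it was judged related to any study treatment. On that pattern 5/9 = 56% of patients with a late CVA would not appear in the 100-day repeats. SAP 8.2.1 itself gives the need to pool several terms for one type of event as a reason for grouping. No planned output combines all causes, all CVA terms and 100 days by arm.

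**The case against.** **The two labels may mean the same thing.** Protocol 8.11 does not mention hemorrhage. Protocol Appendix 6 is oriented to ischemic stroke (DWI MRI, rtPA, a search for emboli), and hemorrhage has separate criteria in 5.14.1.2 and 5.14.1.3. This stands as a reason not to assert a loss. It does not settle the matter, because CVA can include hemorrhage and the search list that would decide it is not in the SAP.

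**No analysis commitment is breached.** Section 8.11 is a reporting rule, 100 days is a collection window, and Protocol 9.6 promises only descriptive tables. The shorter window also matches SAP 8.3.2. All of this is correct. The point is a mismatch between what is collected as the AESI and what is summarised under that name.

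**Stronger readings that the documents do not support.** A reader might infer:
- That the signal *is* under-counted. No hemorrhagic share or late-onset share is given, and the loss could be zero.
- That TIA is dropped. TIA is an ischemic event, so the wording alone does not exclude it.
- That omitted events vanish. Non-ischemic CVAs within the window appear in the TEAE tables by preferred term, and late ones appear at least in listings.
- That crude percentages make the arms non-comparable. Arm A alone is capped at 2 years, so exposure may differ, but neither size nor direction is known. With an equal hazard of 2% per year (assumed) and the 30-day window, the crude risk ratio of Arm A to Arm B is 0.54 for 6 against 12 months of exposure, 1.00 for equal exposure and 1.85 for 12 against 6. The SAP summarises exposure (7.4.4) and time to discontinuation (7.5.3), and its document history shows that an exposure-adjusted ICE analysis was removed on purpose. With about five events, a person-year rate would also be imprecise.

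**Conclusion.** The mismatch in event scope and window is real, and no other planned output closes it. The AESI tables may omit non-ischemic CVAs and CVAs on days 31 to 100 after last dose. With 5.1 Arm A patients expected to have a CVA, each omission is worth about 20% of the estimate. Under the assumed shares in the working, the tables would keep between 5.1 and 2.7 of those events. The range rests on assumptions and includes no loss at all. The expected count assumes that the program's 1.7% applies to this trial's population, follow-up and CVA mitigation measures. The change is worth making because it is specific and nearly free, not because a bias has been shown. The absence of person-year rates is a trade-off and not an error.

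**What to change.** In SAP 8.3.1:
- Define the AESI summary as all CVA and TIA terms, matching Protocol 8.11, with ischemic and hemorrhagic subsets.
- Fix the search list before database lock.
- Repeat the existing ICE tables to 100 days after last dose, once with and once without the cut at new anticancer therapy. The SAP's extended period alone would not do this, because it also stops at new therapy.

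Person-year rates by arm are an optional supportive addition. SAP 7.7 already defines a suitable denominator, to last dose + 100 days, for hospitalizations.

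The cost is SAP wording, a wider search list and a few more table runs. Collection already runs to day 100, so no new data are needed and no clinical rule changes.

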8.3.2 Other Safety Observations (OSO) for NKTR-214

Other safety observations (OSO) for NKTR-214 consists of the following:

- IL-2 mediated AEs
 - Flu-like symptoms
 - Rash and pruritus
 - Fatigue/asthenia
 - Arthralgia
 - Elevated hepatic transaminases
 - Elevated serum creatinine
 - Eosinophilic disorders
 - Hypotension
 - Syncope
- Infusion-related reaction (IRR, same day or next day post study drug administration)
- Cytokine release syndrome/cytokine storm (CRS)
- Capillary leak syndrome (CLS)
- Tachyarrhythmias (including supraventricular and ventricular)

All analyses will be conducted in the Safety I/P-risk population and the Safety all-risk population by treatment arm using the treatment-emergent period.

Table 6 lists the planned analyses for each category of OSO for NKTR-214.

- 1) Overall summary of OSO by worst CTC grade presented by category/PT (any grade, grade 3-4, grade 5).
- 2) Overall summary of serious OSO by worst CTC grade presented by category/PT (any grade, grade 3-4, grade 5).
- 3) Overall summary of OSO leading to discontinuation of any study drug by worst CTC grade presented by category/PT (any grade, grade 3-4).
- 4) Overall summary of OSO leading to discontinuation of NKTR-214 by worst grade presented by category/PT (any grade, grade 3-4). This summary will be conducted for Arm A patients.
- 5) Time-to onset of OSO (any grade, grade 3-5) by category
- 6) Overall summary of OSO by Cycle by Worst Grade by category (any grade, grade 3-5) (for Arm A only, and cycle is every 3 weeks in this analysis)

Time-to onset analyses are restricted to treated patients who experienced at least one OSO in the specific category.

For IRR, events that start after study drug administration on the same day or next day will be included. If AE onset time is available, the time information will be used to exclude events that start before study drug administration; otherwise, AEs that start on the same day as study drug administration will be included. Analysis on IRR will only be performed for Arm A.

A by-patient listing of OSO will be provided.

Table 6: Planned Analyses for OSO for NKTR-214

Table Numbers ^a	Tachyarrhythmias	Syncope	CRS CLS	Infusion-related reaction (same day or next day post study drug administration) (For Arm A only)	Flu-like symptoms; Rash and pruritus; Fatigue/asthenia; Arthralgia; Elevated hepatic transaminases; Elevated serum creatinine; Eosinophilic disorders; Hypotension
1), 2)	Yes	No	No	Yes	Yes
3), 4)	Yes	No	No	Yes	Yes
5)	Yes	Yes	Yes	Yes	Yes
6)	No	Yes	No	Yes	Yes

Abbreviations: CLS = capillary leak syndrome; CRS = cytokine release syndrome/cytokine storm

a. Table descriptions provided in Section 8.3.2.

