6.0 STATISTICAL CONSIDERATIONS

6.1 General Considerations

Although this is an open label study, analyses for treatment comparisons prior to final database lock will not be performed except for the pre-planned interim safety and efficacy analyses as described in Section 11.0 of this document and in the DMC charter.

Blinding for aggregated treatment information during the trial and data unblinding for interim analysis and after final database lock are provided in the Aggregate Data Handling Plan.

Summary statistics for continuous variables will include the mean, standard deviation, median, minimum, and maximum. The mean and median will be presented to one decimal place beyond which the data were captured. The standard deviation will be presented to two decimal places beyond which the data were captured. The minimum and maximum will be presented to the precision with which the data were captured.

Categorical variables will be presented as frequency counts and percentages. A row or column denoted 'Missing' will be included in count tabulations where necessary to account for dropouts and missing values. Percentages will be rounded to 1 decimal place and the percent will be suppressed when the count is zero. The denominator will be the number of patients in the population of interest unless otherwise noted.

Time-to-event variables will be analyzed using the Kaplan-Meier (KM) method. The KM estimates for 25th, 50th (median) and 75th percentiles with associated 2-sided 95% confidence interval using Greenwood's formula ([Greenwood, 1926](#)), as well as the percentage of censored observations will be presented. All time-to-event variables will be plotted using the KM method.

Data listings will be created to support each table and to present all data. Data listings will be presented by treatment group and patient number.

[figure not shown]

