6.3 Analysis Populations

Intent-to-Treat (ITT) IMDC Intermediate- or Poor-risk Population: All patients who are randomized and are classified as intermediate- or poor risk according to the IMDC prognostic score entered in the IRT system at randomization. Patients are grouped by the treatment to which they are randomized. It is abbreviated as ITT I/P-risk Population in the document.

ITT IMDC All-risk Population: All patients who are randomized. Patients are grouped by the treatment to which they were randomized. It is abbreviated as ITT All-risk Population in the document.

Safety IMDC Intermediate- or Poor-risk Population: All patients who receive at least 1 dose (or partial dose) of any study drug and are classified as the intermediate- or poor-risk according to the IMDC prognostic score entered in the IRT system at randomization. Patients are grouped according to the treatment they actually received. It is abbreviated as Safety I/P-risk Population in the document.

Safety IMDC All-risk Population: All patients who receive at least 1 dose (or partial dose) of study drug. Patients are grouped according to the treatment they actually received. It is abbreviated as Safety All-risk Population in the document.

Objective Response Rate (ORR) IMDC Intermediate- or Poor-risk Population: All randomized patients classified as the intermediate- or poor-risk according to the IMDC prognostic score who have at least 6 months of follow-up at the time point of the ORR analysis. A patient's follow-up time is defined here as the time between randomization date and clinical data cutoff date regardless of patient disposition (i.e., ITT principle). Patients are grouped by the treatment to which they were randomized. This analysis population will be equivalent to the ITT IMDC Intermediate- or Poor-risk Population if the clinical data cutoff date is at least 6 months after the date that the last patient was randomized. It is abbreviated as ORR I/P-risk Population in the document.

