7.6.2 EQ5D3L

The EQ-5D-3L is a standardized instrument used to measure self-reports of health status and functioning. The instrument's descriptive system consists of 5 dimensions: mobility, self-care, usual activities, pain/discomfort, and anxiety/depression. Each dimension has 3 levels, reflecting "no health problems," "moderate health problems," and "extreme health problems." A dimension for which there are no problems is said to be at level 1, while a dimension for which there are extreme problems is said to be at level 3. Thus, the vectors 11111 and 33333 represent the best health state and the worst health state, respectively, as described by the EQ-5D-3L. Altogether, the instrument describes $3^5 = 243$ health states (EuroQol, 1990).

Empirically-derived weights can be applied to an individual's responses to the EQ-5D-3L descriptive system to generate an index measuring the value to society of his or her current health. Such preference-weighting systems have been developed for the UK, US, Spain, Germany, and numerous other populations. Utility index values range from a 1 (full health) to 0 (dead) with negative values indicating a state considered worse than being dead. In addition, the EQ-5D-3L includes a visual analog scale (VAS) that allows respondents to rate their own current health on a 101-point scale ranging from "best imaginable" to "worst imaginable" health. The EQ-5D-3L uses a recall period of "today."

EQ-5D Index values will be computed using a scoring algorithm based on the US TTO (Time Trade-off) value set. The following descriptive analyses will be conducted:

- EQ-5D questionnaire completion rate, defined as the proportion of questionnaires actually received out of the expected number (ie, number of patients on treatment or in follow up), will be calculated and summarized for each assessment time point.
- A by-patient listing of EQ-5D with the problem level for each of the 5 dimensions (mobility, selfcare, usual activities, pain/discomfort and anxiety/depression), health state (5 dimensions digits combined in a 5-digit number), EQ-5D Index, and EQ-VAS will be provided.
- Proportion of patients for each level of problem for the 5 EQ-5D dimensions will be summarized at each assessment timepoint. Percentages will be based on number patients assessed at assessment time point.
- For the EQ-5D Index and visual analog scale (VAS), separately:

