immunogenicity evaluable population, the patients will be classified as treatment-induced ADA-positive if they were ADA-negative at baseline and became ADA-positive at any time after starting the treatment, or if they were ADA-positive at baseline and had a post-baseline ADA-positive titer that was at least 4-fold or greater (\geq) than baseline positive titer (also known as Treatment-boosted). The patients with an ADA-positive sample at 2 or more consecutive time points, where the first and last ADA-positive samples are at least 16 weeks apart will be classified as persistent positive. Patients that are not persistent positive but have an ADA-positive sample at the last sampling time point will be classified as not persistent last-sample positive. Non persistent positive patients with an ADA-negative sample at the last sampling time point will be classified as transiently positive or other positive. Patients with at least 1 ADA-positive sample with neutralizing activity will be classified as neutralizing positive. All other ADA-evaluable patients are considered as treatment-emergent ADA negative.

All ADA-positive patients will be included in the ADA titer kinetics analysis. Summary statistics of patient-level ADA titers using the maximum titer value within an ADA-positive patient will be presented for baseline ADA-negative patients and baseline ADA-positive patients. The median, interquartile range, and range of the maximum titers will be reported. For ADA-positive patients with baseline ADA-positive sample, the median and interquartile range of the fold increase from baseline in titer (ratio of maximum post-baseline titer to baseline titer) will also be reported. For sample-level ADA titers, boxplots of ADA titers at each assessment timepoint will be provided, as appropriate, to demonstrate whether the ADA levels tend to change over time during the treatment, along with ADA incidence at each assessment timepoint.

Analyses of ADA kinetics, including the onset and duration of ADA, will include only those ADA-positive patients that were ADA-negative at baseline. ADA-positive patients with baseline ADA-positive sample and an increased titer post-baseline will be excluded since this type of immune response differs mechanistically.

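### SAP 8.3.2, analysis 6: the by-cycle table of NKTR-214 safety observations takes the default whole-population denominator, so later-cycle percentages fall as patients leave treatment

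*SAP*

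**What the plan says.** SAP 8.3.2 lists six analyses of other safety observations (OSO). The sixth is "Overall summary of OSO by Cycle by Worst Grade by category (any grade, grade 3-5"), with the note "for Arm A only, and cycle is every 3 weeks in this analysis". SAP Table 6 applies it to syncope, infusion-related reactions and the eight grouped IL-2-type categories, but not to tachyarrhythmias, cytokine release syndrome or capillary leak syndrome.

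The population for the section is set in one sentence: "All analyses will be conducted in the Safety I/P-risk population and the Safety all-risk population by treatment arm using the treatment-emergent period". SAP 6.3 defines the all-risk Safety population as "All patients who receive at least 1 dose (or partial dose) of study drug", with no requirement to be on treatment or under observation at a given time. The intermediate/poor-risk version adds only the risk-group condition.

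SAP 6.1 supplies the rule for percentages: "Categorical variables will be presented as frequency counts and percentages", and "The denominator will be the number of patients in the population of interest unless otherwise noted". Neither analysis 6 nor Table 6 notes anything else. The only restriction added in 8.3.2 on who is included concerns time to onset, which is analysis 5.

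SAP 6.6 limits which events count. For a patient off treatment, the treatment-emergent period shuts at the earlier of 30 days past the final dose of any study drug and the day before new anticancer therapy.

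**The concern.** After the treatment-emergent window closes, a patient can add nothing to the numerator of any later cycle but remains in the default denominator. The reported percentage for a late cycle is then the product of two things: the risk among patients still under observation, and the share of patients still under observation.

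The SAP redefines a cycle as 3 weeks for this table, whereas the protocol's treatment cycle is 6 weeks. Three weeks is the dosing interval, so the table's evident use is to show how toxicity behaves over successive doses. With a fixed denominator, a flat risk looks like a declining one, which could be read as growing tolerance. Equally, a real early-onset pattern, such as the one protocol 5.13.4 describes for transaminase elevations in Cycles 1 and 2, cannot be told apart from attrition.

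**Working it through.** The documents state no figure for this table, so there is none to reproduce. The check has two parts.

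**1. Which denominator applies.**

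- SAP 6.1 gives a default stated in patients, open to override.
- SAP 8.3.2 names the population for all its analyses, and SAP 6.3 defines that population by a single dose.
- No override appears in analysis 6 or Table 6.
- The SAP does state another base where it wants one. For EQ-5D-3L dimensions (7.6.2): "Percentages will be based on number patients assessed at assessment time point". Hospitalizations in 7.7 use person-years. Laboratory summaries in 8.5 require a baseline and a treatment-emergent value.

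Read as written, each cycle in analysis 6 is divided by all Arm A Safety patients.

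**2. How much this can distort.** If *p* is a constant per-cycle risk among patients under observation and *F(c)* is the share of Arm A still in the treatment-emergent window at the start of cycle *c*, then

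reported rate = *p* × *F(c)*, so reported/true = *F(c)*, whatever *p* is.

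Inputs from the documents:

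- 3-week (21-day) cycles (SAP 8.3.2).
- A 30-day window after the last dose of any study treatment (SAP 6.6).
- 300 patients planned per arm (protocol synopsis).
- A 2-year limit on Arm A treatment (protocol 5.4.3), about 104/3 = 34.7 three-week cycles.

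Assumptions, not in the documents: exponential time on all study treatment, with median *m* of 6, 9 or 12 months; all 300 patients dosed; the same risk in the 30-day tail as on treatment; no early closure of the window by new therapy.

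*F(c)* = exp{−ln 2 × [(c − 1) × 21 − 30] / (30.4375 × m)} once (c − 1) × 21 exceeds 30.

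Days entering the formula: cycle 3, 42 − 30 = 12; cycle 9, 168 − 30 = 138; cycle 17, 336 − 30 = 306.

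| Cycle | m = 6 months | m = 9 months | m = 12 months |
|---|---|---|---|
| 3 | 0.96 | 0.97 | 0.98 |
| 9 | 0.59 | 0.71 | 0.77 |
| 17 | 0.31 | 0.46 | 0.56 |

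For example, at cycle 17 with m = 6: exp(−0.6931 × 306 / 182.6) = exp(−1.161) = 0.31. About 94 of 300 patients are then still in the window. A true 10% risk gives about 9.4 patients with an event, reported as 9.4/300 = 3.1%.

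Infusion-related reactions count only on the day of study drug administration or the next day, so the 30-day tail does not help. Dropping the 30 days from the formula gives the share still on treatment: 0.53, 0.65 and 0.73 at cycle 9, and 0.28, 0.43 and 0.53 at cycle 17, for m = 6, 9 and 12.

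**The case against.** The strongest reply is that the error is inferred from silence. The 6.1 default refers to a population of interest, which for a by-cycle row could be taken to mean patients in that cycle. Protocol 5.13 ties Arm A dosing visits to drug administration, so someone who never starts a cycle arguably has no such cycle. The EQ-5D-3L sentence might show the authors' general habit for time-point percentages, and table shells may already use a per-cycle n. The shells cannot be ruled out. But 8.3.2 does name its population, and the SAP writes down a different base elsewhere when it intends one. If a per-cycle n is intended, the SAP should say so.

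A second reply is that the table is descriptive, covers Arm A only and involves no test. Overall and serious incidence come from analyses 1 and 2, a by-patient listing is planned, and SAP 7.5.3 plans a Kaplan-Meier summary of time to NKTR-214 discontinuation. All of that stands and limits the importance of the point. None of it corrects the percentages in the table itself.

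Three stronger readings are tempting and are not supported:

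- **That patients leave the risk set when they stop NKTR-214.** The SAP 6.6 window runs from the last dose of any study treatment, and SAP 5.2.1 and protocol 5.13 allow nivolumab to continue alone. Such patients can still have treatment-emergent events. A bias factor based on NKTR-214 discontinuation would overstate the early dilution, and a denominator of patients given NKTR-214 in the cycle would not match the numerator.
- **That ADA incidence has the same fault.** SAP 7.8.1 asks for boxplots of sample-level titers "along with ADA incidence at each assessment timepoint", and the section reports by sample as well as by patient. A per-sample base is a natural reading, so a patient-denominator error is not established there.
- **That any fall across cycles would be artefact.** The protocol itself expects some early clustering. Even a correct denominator would not remove selection, because patients who stop for toxicity leave it.

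**Conclusion.** The point holds for analysis 6 of SAP 8.3.2 only. Followed as written, the plan divides every 3-week cycle by the whole Arm A Safety population, so late-cycle percentages understate the risk among patients still under observation.

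The direction follows from the SAP's own rules. The size does not, because the documents give no discontinuation rates. Under the assumed 6- to 12-month exponential medians and with the 30-day window counted, the distortion is slight at cycle 3 (reported at 96-98% of true) but substantial at cycle 9 (59-77%) and cycle 17 (31-56%). Longer time on treatment would shrink it. Window closure by new anticancer therapy would enlarge it.

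This is a minor correction to one descriptive safety table. No primary or key secondary endpoint depends on it.

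**What to change.** In SAP 8.3.2, analysis 6, state that:

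- the denominator for each 3-week cycle is the number of Arm A Safety patients still in the treatment-emergent period at the start of that cycle, so that it matches the treatment-emergent numerator;
- for infusion-related reactions, the denominator is the number of patients who received an infusion of study drug in that cycle;
- the n used is printed for each cycle.

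The text should also say how the 3-week cycles are bounded when dosing is delayed or has stopped, since the denominator is counted at the start of each cycle.

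The cost is a few sentences and a changed table denominator, with no new data. The downside is that late-cycle percentages will rest on fewer patients and look less favourable.
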